11.4 Statistical Analyses

Statistical analysis described in this section will be based on the PK statistical population.

11.4.1 *PK Parameters in Plasma*

Individual, mean and median plasma concentration versus time curves will be presented for both linear and semi-log scales. Descriptive statistics (arithmetic and geometric means, SD, CV%, geometric mean CV%, Min, Max, and median) of the plasma concentrations versus time will be presented as well for the PK parameters.

11.4.2 *Treatment Comparisons*

For zavegepant, using the MIXED procedure in SAS, an ANOVA will be performed on ln-transformed (dose-normalized to 100 mg) AUC_{last} , AUC_{inf} , and C_{max} . No adjustments will be made to alpha for multiple pairwise comparisons. As the study was dosed in more than one Group, the following terms will be included in the statistical model: Group, Sequence, Sequence by Group, Period within Group, Treatment, and Treatment by Group. A random effect of Participant within Sequence by Group will also be included. In case of a non-statistically significant Treatment by Group interaction term, the analysis will be rerun excluding this term from the ANOVA model in order to obtain ratios and confidence intervals where appropriate. The ratio of geometric means and 90% confidence intervals (A/D), (B/D), and (C/D) based on least-squares means from the ANOVA of the ln-transformed data will be calculated for AUC_{last} , AUC_{inf} , and C_{max} . The point estimates and confidence intervals will be exponentiated using base e in order to obtain a point and interval estimate for the ratio of geometric means. Other ratio of geometric means among treatments may be explored. Untransformed T_{max} will also be analyzed using the MIXED model with the difference of least-squares means from the ANOVA calculated for (A-D), (B-D), and (C-D). Other differences of least-square means between treatments may be explored. The K_{el} , and $T_{1/2}$ will be summarized descriptively.

The SAS code to fit the model will follow the format below (using the Mixed Procedure). The input variables, datasets, and labels are depicted in italicized red text and have been given generic names.

This document is confidential.

```
proc mixed data = basepk;
  class Group Sequence Period Treatment Participant;
  model VAR = Group Sequence Sequence*Group Period(Group) Treatment
    Treatment*Group / ddfm = kenwardroger;
  random Participant (Sequence*Group);
  lsmeans Treatment;
  estimate 'A versus D' Treatment 1 0 0 -1 / cl alpha = 0.1;
  estimate 'B versus D' Treatment 0 1 0 -1 / cl alpha = 0.1;
  estimate 'C versus D' Treatment 0 0 1 -1 / cl alpha = 0.1;
  ods output estimates = estimates tests3 = tests covparms = covparms;
run;
```

Additional PK statistical analysis may be performed.

This document is confidential.

12 PERCENTAGES AND DECIMAL PLACES

Percentages:

Percentages based on count data should be displayed as follows in TLFs:

- $0 < \text{percentage} < 0.1$ as “<0.1”
- $99.9 < \text{percentage} < 100$ as “>99.9”
- 100 percentage as “100”
- 0 count without a percentage in frequency tables
- Rounded to 1 decimal place otherwise.

For response rates (proportions), measures of variability such as standard error (SE) and confidence interval (CI) should be displayed rounded to 1 decimal place.

Continuous Variables Non-PK Data:

Descriptive statistics for continuous variables in tables should be displayed as follows:

- Values and changes from baseline
 - Minimum and maximum: same precision as the data collected or rounded to a specified precision if derived
 - Mean and percentiles: rounded to 1 decimal place more than the data collected or derived
 - Measure of variability (e.g., standard deviation [SD], SE, CI): rounded to 2 decimal places more than the data collected or derived
- Percent change from baseline
 - Minimum and maximum: rounded to 0 decimal places (i.e., integers)
 - Mean and percentiles: rounded to 1 decimal place
 - Measure of variability: rounded to 2 decimal places.

Individual data in listings should be displayed to the same precision as the data collected or rounded to a specified precision if derived.

Derived variables should be calculated using all precision from collected components. For example, BMI should be derived as needed using all precision from collected height and weight. However, the specified precision for reporting BMI should be 1 decimal place.

Continuous Variables PK Data:

Concentration data for parameter calculations: The concentration data as reported by the respective bioanalytical groups should be used, without rounding, for all analyses.

This document is confidential.

Concentration data listings: By default, concentration values should be presented in listings exactly as reported by the respective bioanalytical groups. However, in cases when concentration data may be supplied electronically with unrealistic precision, rounded values may be presented. A default of 3 significant figures is suggested, and the rounding used should be described in the clinical study report.

Parameter data listings: The non-compartmental parameters should not be reported to any greater precision than that of the concentration data. A default of 3 significant figures is preferred.

Concentration and parameter summary data: The following guidance for reporting precision is intended to provide specifications for programming and defaults for documents based on those presentations. It is recognized that data from external sources may follow different standards. Refer to below for additional guidance on parameter summary statistics for study report and summary documents.

Parameter values (and if applicable, concentration values) should be rounded to the same precision used in data listings prior to any statistical analysis or descriptive summaries.

Descriptive summaries:

- Means, median^a, CIs - 1 more significant figure than the data
- SD - 1 more significant figure than means
- CV% - whole numbers
- Min, Max - same significant figures as the data

^a Exception: for T_{max} , T_{lag} , and any other parameters which are direct time observations, median will have the same significant figures as the data (mean is generally not presented for these parameters).

Statistical summaries:

- Means, differences, CIs (non-transformed data) - 1 more significant figure than the data.

This document is confidential.

13 DATA HANDLING

For the final analyses, the PK, safety, and tolerability data will be received as SAS datasets. Screening failures and ineligible volunteer's data (participant disposition) will be received from the clinical site as source data.

This document is confidential.

14 MISSING DATA

There will be no imputation for missing data, unless otherwise specified. Missing data will be presented in participant listings as either “-” (unknown or not evaluated) or “N/A” (not applicable), with the corresponding definition in the footnotes. Missing descriptive statistics, or probability values (p-values), which cannot be estimated will be presented as “-”.

Incomplete AE start and stop dates will be imputed as follows:

- If an AE is recorded with an onset date corresponding to a dosing day, but the time is missing, then the AE will be assigned to that day treatment (e.g., an AE with an onset date on Day 1 without time will be allocated to the treatment received on Day 1, and considered treatment-emergent).
- If an AE is recorded with an onset date that does not correspond to a dosing day, but the time is missing, then the AE will be assigned to the planned treatment that covers the AE onset day and considered treatment-emergent if onset date is after the date of first dosing.
- If an AE is recorded with an onset date where day and time are both missing, then the AE allocation to the planned treatment will be done on a case-by-case basis considering available information (i.e., AE recording date, AE end date, AE comments, participant disposition).

For PK analysis, only observed concentration data will be used in the data analysis, except for concentration values BLQ as described in [section 11.1](#). No attempt will be made to extrapolate or interpolate estimates for missing data.

This document is confidential.

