3.5 Participant Withdrawal and Replacement

Over the course of the study, the Sponsor and the Investigator or designee may withdraw any participant from the study for one of the reasons described below; participant withdrawal will be done in accordance with the clinical site's SOP:

- Safety reason;
- Non-compliance with protocol requirements;
- Significant protocol deviation;
- Positive pregnancy test, drug screen, cotinine test, or alcohol breath test;
- Vomiting within 4 hours post-dose;
- Positive COVID-19 test.

Participants excluded from dosing in one period as per criteria listed above, may be invited to participate in subsequent periods of the study if deemed appropriate by the Investigator and appropriate from a statistical standpoint (i.e., would permit adequate statistical comparison). However, participants with positive pregnancy test, COVID-19 test, drug screen, cotinine test, or alcohol breath test will be definitively withdrawn from the study.

Participants experiencing emesis following study drug administration may be withdrawn. An evaluation will be done on a case-by-case basis in order to decide if withdrawal is appropriate.

Participants who withdraw, or are withdrawn, prior to dosing may be replaced. Participants who withdraw, or are withdrawn, from the study after dosing will not be replaced.

This document is confidential.

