6.3 Safety Population

The safety population is defined as all participants who receive at least one dose of any study drug. In each period, participants will be analyzed according to treatment received.

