10.2 Adverse Events

AEs, which are collected from the time of enrollment, will be coded using the latest version of MedDRA (Version 25.0).

All AE summaries will be restricted to treatment-emergent adverse events (TEAEs) only. TEAEs will be defined as AEs that occur on or after the date and time of first study drug administration. Any AE that first occurs prior to first study drug administration but worsens in severity after the first study drug administration will also be considered a TEAE. Non-TEAEs are those that occur prior to the first administration of the study medication and resolved prior to dosing or that first occur prior to the first study drug administration, but do not worsen in severity after dosing. TEAEs will be attributed to the most recent study drug taken. A TEAE with a start date and time during the washout period (ending at the time of next study drug administration) will be attributed to the study drug taken during the previous treatment period (unless there was worsening following the next drug administration).

TEAEs will be summarized by treatment for the safety population. The number and percentage of participants experiencing TEAEs and the number of TEAEs will be tabulated. Participants who experience the same AE (in terms of MedDRA PT) more than once will only be counted once for that event, however, the total number of events will also be counted per category. This also applies to sub-categories and SOCs displayed in the summaries.

In each table, TEAEs will be sorted by SOC and PT in descending order of overall frequency. The following summaries will be presented:

- Overall summary of TEAEs

This document is confidential.

- TEAEs by SOC and PT
- TEAEs by SOC, PT, and maximum severity
- TEAEs by SOC, PT, and maximum relationship to study drug
- Serious TEAEs by SOC and PT

All AEs will be presented in data listings. This will include a separate listing of TEAEs, Non-TEAEs and serious AEs. AEs leading to discontinuation will also be listed separately.

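### SAP 14 allocates adverse events with no onset time to the planned treatment, so an event in a period where dosing was missed can be counted under a product never taken (minor)

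*SAP*

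**What the plan says.** Three parts of the SAP say which treatment an adverse event belongs to.

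- SAP 6.3 (Safety Population): "In each period, participants will be analyzed according to treatment received".
- SAP 10.2 (Adverse Events): "TEAEs will be attributed to the most recent study drug taken". An event starting in the washout, which ends at the time of the next administration, "will be attributed to the study drug taken during the previous treatment period", unless it worsens after the next dose.
- SAP 14 (Missing Data) has three bullets for incomplete onset. On a dosing day with no time, the example has the event "allocated to the treatment received on Day 1". On a non-dosing day with no time, the event is "assigned to the planned treatment that covers the AE onset day". With day and time both missing, "the AE allocation to the planned treatment will be done on a case-by-case basis", using available information such as participant disposition.

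Section 14 does not define *covers*. Nothing in the SAP says that 10.2 prevails over 14, or that *planned* is meant as *received*.

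Planned and received treatment can differ by design. Under SAP 3.5, matching Protocol 4.4, participants excluded from dosing in one period "may be invited to participate in subsequent periods of the study", subject to the investigator's judgement and to statistical suitability.

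**The concern.** Two sections make the drug actually taken the basis of attribution, and a third switches to the drug that was scheduled. The switch applies to the events for which section 14 is the specific rule, so a programmer following the SAP literally would apply it.

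The missing time does not call for the switch. No dose is given on a non-dosing day, so the date alone identifies the last dose taken. The planned treatment therefore either repeats the answer from 10.2 or contradicts it.

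At stake is the table of treatment-emergent events by treatment, the plan's tolerability summary for the four products. A participant who missed a dose could appear as having an event under that product. If column denominators are the participants who received the product, as 6.3 implies, that participant would be in the numerator but not in the denominator.

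**Working it through.** The plan gives no figure on this point, so there is nothing to reproduce. The check compares the two rules day by day.

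**Rules.** For an event with onset on day *d*, a day without a dose:

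- p(d) = the treatment that the sequence assigns to the period containing *d* (SAP 14);
- r(d) = the treatment of the latest dose actually taken before *d* (SAP 10.2).

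**Inputs.** The sequences are ACBD, CDAB, BADC and DBCA (SAP 3.1). The washout is at least 7 days between doses (Protocol 3). I assume doses on study days 1, 8, 15 and 22, the shortest schedule allowed, and examine days 2 to 23, which is 22 days. Taking out dosing days 8, 15 and 22 leaves 22 − 3 = 19 days without a dose. If one of those doses is missed, 22 − 2 = 20 days remain.

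**Two readings of the period.** In the dose-to-dose reading, a period runs from its dosing day to the day before the next dosing day, in line with the washout window in 10.2. In the visit reading, Day -1 belongs to the upcoming period, as the column layout of Protocol Table 1 might suggest.

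**Worked case.** Take sequence ACBD with Period 2 not dosed. An event starts on day 10 with no time. Then p(10) = C and r(10) = A. The participant takes A, B and D and never takes C. The same holds for each of days 8 to 14, which is 7 days. One of these is day 8, the scheduled dosing day on which no dose was given; without it the count is 6.

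**Days per sequence on which p(d) and r(d) differ** (the same for all four sequences, because each gives four different treatments):

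| Dosing | Reading | Days without a dose | Disagree | To a product never taken | To a product not yet taken |
|---|---|---|---|---|---|
| All four taken | Dose to dose | 19 | 0 | 0 | 0 |
| Period 2 or 3 missed | Dose to dose | 20 | 7 | 7 | 0 |
| Period 4 missed | Dose to dose | 20 | 2 | 2 | 0 |
| All four taken | Day -1 in upcoming period | 19 | 3 | 0 | 3 |
| Period 2 or 3 missed | Day -1 in upcoming period | 20 | 9 | 7 | 2 |
| Period 4 missed | Day -1 in upcoming period | 20 | 5 | 3 | 2 |

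The Period 2 or 3 rows are the miss-and-return case. Under the dose-to-dose reading, which is the one kinder to the plan, every disagreement sends the event to a product never taken. The 3 disagreements with all doses taken are Day -1 of Periods 2, 3 and 4, and they arise only under the visit reading.

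**Size per event.** With 52 participants exposed to a product, moving one changes a percentage by 1/52 = 0.0192, about 1.9 points. If 52 are dosed and one misses a product, at most 51 receive it, and the figure is 1/51 = 0.0196, about 2.0 points. Up to two columns move: one loses the participant and one gains. SAP 10.2 counts a participant once per preferred term, so a column does not change if that participant is already counted there for the same term.

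**The case against.** The strongest reply concerns Day -1. Laboratory tests, ECG, physical examination and vital signs are all scheduled on Day -1 of each period, so a reader might infer that timeless Day -1 findings in Periods 2 to 4 are always credited to the next product, and that misallocation is therefore routine. The documents do not support that. Protocol Table 1 is a visit schedule, not an attribution rule. The only attribution window that the SAP defines is in 10.2, where the washout ends at the next administration. On that window Day -1 of Period 2 belongs to the Period 1 treatment, which is correct, and with all doses taken the rules never disagree. What remains is that *covers* is undefined and two programmers could code it differently.

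The missed-period case is also narrow. Dosing must be missed for a reason that allows return (a positive pregnancy, COVID-19, drug, cotinine or alcohol test does not), the return must be approved, and an event must start in that window without a recorded time. The documents give no rate for any of these steps. This limits how often the rule matters, but not what it does when it applies.

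It can also be said that 6.3 already requires treatment received, and that the third bullet of section 14 looks at participant disposition, so a missed dose would be noticed. That helps only partly. The second bullet has no such check, the third still names the planned treatment as the target, and no order of precedence is stated.

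Finally, the first bullet can credit an event that began before the dose on Day 1 of Periods 2 to 4 to that day's drug. This is true, but it is a different matter: on a dosing day the date cannot settle the order, so some convention is needed.

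**Conclusion.** Wrong as written, and minor. The planned-treatment wording in the second and third bullets of SAP 14 contradicts SAP 6.3 and 10.2. When a participant misses dosing in a period and returns, the second bullet taken literally counts a timeless event from that period under a product never taken. This does not depend on how Day -1 is read. The day counts rest on the assumed 7-day spacing; with longer gaps between doses they would change, but the contradiction would not.

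The Day -1 question is an ambiguity, not a demonstrated error.

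The consequence is limited. Only events without an onset time, or without both day and time, are affected. The shift is about 1.9 points per moved participant per affected column with 52 exposed, and nothing where the participant is already counted for that term. Safety is a secondary endpoint (SAP 5) analysed descriptively (SAP 10), and all events and dosing times are listed by participant, so an allocation can be traced. The study's sole objective is rate and extent of absorption, and no PK result depends on this rule.

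**What to change.** In SAP 14:

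- Second bullet: in place of "assigned to the planned treatment that covers the AE onset day", write *assigned to the most recent study drug actually received before the AE onset date*. Day -1 of Periods 2 to 4 then goes to the preceding treatment received, and *covers* no longer needs a definition. The condition for calling the event treatment-emergent can stay as it is.
- Third bullet: change *planned treatment* to *treatment received*, keeping the case-by-case review.

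This brings section 14 into line with 6.3 and 10.2. It costs two small wording changes in the SAP and the matching program line, with no new data and no effect on the PK analysis.

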15 SOFTWARE

All tables, figures, and listings and statistical analyses will be generated using SAS for Windows, release 9.4 (SAS Institute Inc., Cary, NC, USA) software in accordance with Food and Drug Administration (FDA) guidelines.

Phoenix WinNonlin, version 8.3.4 (Certara USA, Inc., Princeton, NJ) will be used for all PK analyses. This software was validated by Syneos in compliance with US 21 CFR Part 11 regulation.

This document is confidential.

